#### 2.2 IACS-010579

#### 2.2.1 IACS-010759 Preclinical Biology

IACS-010759 inhibits complex I of mitochondria oxidative phosphorylation (OXPHOS). IACS-010759 is a potent inhibitor of the proliferation of human cancer cells, including AML cell lines, human primary AML cells, and glycolysis-deficient NB-1 neuroblastoma cells. Both primary AML

Page 14 of 59

cells and established cell lines demonstrated dose-dependent growth inhibition and reduction of cell viability in response to IACS-010759, with IC $_{50}$  values ranging from 1-10 nM. Ectopic expression of the yeast complex I protein NDI-1 partially restored AML cell viability, indicating that the effects of IACS-010759 were mechanism-based *via* OXPHOS inhibition. In contrast to the potent effect of IACS-010759 on the viability of tumor cells, the compound had minimal effects on the viability of bone marrow cells obtained from healthy subjects, suggesting that the compound has a therapeutic window for tumor cells *vs.* normal leukocytes.

The sensitivity of NB-1 cells, which lack the gene that encodes the essential glycolytic pathway enzyme phosphogluconate dehydrogenase (PGD), to IACS-010759 was reduced upon ectopic expression of PGD. This suggests that the sensitivity of NB-1 cells to IACS-010759 is due to their inability to upregulate glycolysis in response to energy stress conferred by IACS-010759 treatment. This is consistent with the OXPHOS inhibitory mechanism of IACS-010759 and with the observed increase in potency of IACS-010759 to kill AML cells compared to normal bone marrow cells.

IACS-010759 inhibits tumor growth and extends survival in AML xenograft models. IACS-010759 caused dose-dependent tumor regression or substantial tumor growth inhibition (TGI) in both orthotopic and subcutaneous xenograft models with human AML and NB-1 neuroblastoma cells, while overall survival was increased in both primary AML and OCI-AML3 cell line orthotopic xenograft models.

In these *in vivo* efficacy experiments, increases in dose or shortening of the dosing interval corresponded to increases in efficacy, measured as TGI or regressions. Notably, in all studies, decreases in dosing frequency at a given dose correspond to decreases in efficacy, with QD dosing being more effective than intermittent dosing of the same dose of IACS-010759.

Trough plasma levels at steady state of 10-20 nM (5.6-11.3 ng/mL) were associated with efficacy in these xenograft studies, regardless of the dosing regimen. This concentration correlates well with the IACS-010759 concentrations of 1-10 nM that are required to inhibit cancer cell proliferation and to inhibit the OXPHOS pathway in cell based assays *in vitro*. Based on these preclinical efficacy studies, it seems reasonable to target sustained trough steady state plasma levels of 10-20 nM (5.6-11.3 ng/mL) IACS-010759 for efficacy in human clinical trials.

#### 2.2.2 IACS-010759 Nonclinical Experience

The pharmacological, pharmacokinetic, and toxicological properties of IACS-010759 were characterized in a series of completed and ongoing nonclinical studies. These studies demonstrate that:

- IACS-010759 inhibits proliferation and reduces the viability of primary human AML samples treated *ex vivo* and in AML cell lines with IC₅₀ values ranging from 1-10 nM, and has minimal effects on the viability of bone marrow cells obtained from healthy subjects. These studies suggest that IACS-010759 has a therapeutic window for tumor cells vs. normal leukocytes.
- IACS-010759 caused dose-dependent tumor regression or substantial tumor growth inhibition (TGI) in both orthotopic and subcutaneous xenograft models with human AML and NB-1 neuroblastoma cells. In addition, survival was increased in both primary AML and OCI-AML3 cell line orthotopic xenograft models. Several oral dosing regimens were explored in these studies, and efficacy was consistently observed with steady state trough plasma levels of 10-20 nM (5.6-11.3 ng/mL) IACS-010759.

- IACS-010759 had negligible inhibitory activity (estimated IC50 > 30  $\mu$ M) at hERG K+ channels and did not prolong the QTc interval in monkeys at doses up to 1.5 mg/kg/day for up to 28 days.
- IACS-010759 did not elicit central nervous system effects in rats treated with oral doses up to 2 mg/kg based on neurobehavioral parameters (functional observation battery).
- IACS-010759 exhibited low plasma clearance, a high volume of distribution, and a long half-life (42 to 57 hours) in mice, rats, dogs, and monkeys. Upon oral dosing, the compound was absorbed relatively slowly, with Tmax values in the range of 3 to 8 hours and bioavailability of ~100% in mouse and rat and ~36% in monkey.
- IACS-010759 exhibited low/moderate metabolic turnover following incubation with liver microsomes and hepatocyte preparations from mouse, rat, dog, monkey and human. No metabolites unique to human were identified. IACS-010759 was found to be a moderate competitive inhibitor of CYP 2C19 (IC50 = 4 uM), but did not inhibit any other CYP isoforms tested. No time dependent inhibition of CYPs 1A2 or 3A4 was observed.
- The potential for CYP enzyme induction by IACS-010759 could not be assessed in standard hepatocyte enzyme induction assays, likely because of the mechanism-based effects of IACS-010759 on oxidative phosphorylation. Therefore, the potential of IACS-010759 to reduce the levels of drugs metabolized by CYP450 enzymatic pathways is unknown.
- In transporter studies, IACS-010759 had no effect on BSEP-, MDR1-, OAT1-, OAT3-, OATP1B1-, OATP1B3- and OTC1-mediated probe substrate transport. IACS-010759 moderately inhibited the BCRP- and OCT-2 mediated probe transport by 27% and 36%, respectively, at 1  $\mu$ M. IACS-010759 is likely a substrate of the BCRP and MDR1 transporters.
- A drug-drug interaction (DDI) study was conducted with IACS-010759 and pentagastrin or the histamine H2 blocker famotidine in dogs. Neither pentagastrin nor famotidine affected the plasma levels of IACS-010759 after oral administration, indicating low potential for DDI with drugs that affect stomach pH.
- IACS-010759 was nongenotoxic in a bacterial reverse mutation assay without or with metabolic activation, and in a bone marrow micronucleus test conducted after 28-days of oral administration in rats at doses up to 2 mg/kg/day, the highest dose tested.
- Single-dose IV administration of IACS-010759 to monkeys showed that sporadic emesis observed following oral and IV administration was a systemic rather than a local GI effect. Plasma levels of IACS-010759 associated with acute emesis were higher than those not associated with emesis.
- IACS-010759 was well tolerated in GLP-compliant 28-day oral toxicity studies in rats and monkeys at doses up to 1 mg/kg/day and 1.5 mg/kg/day, respectively. Higher doses in the 28-day studies and/or 14-day dose range-finding studies resulted in adverse effects in both species, including moribundity requiring euthanasia and/or mortality in rats at ≥2 mg/kg/day and in monkeys at ≥3 mg/kg/day. There were no treatment-related histopathological findings in tissue sections from the 28-day studies.
- Cmax on Day 28 from pivotal toxicity studies was 61.3 ng/mL in rats and 99.3 ng/mL in monkeys at doses of 1 mg/kg/day and 1.5 mg/kg/day, respectively. These Cmax values, which were observed at doses that were well tolerated for 28 days in each species, were notably higher than steady state trough plasma levels of 5.6 11.3 ng/mL at which efficacy was consistently observed in nonclinical xenograft models of human tumor cells. Because the human peak:trough plasma levels with daily oral dosing are projected to be <2-fold based on projected human clearance and on the preliminary data from cohorts 1 and 2 of the

present study, this represents a significant exposure multiple above the projected human exposure required for efficacy.

#### 2.2.3 IACS-010759 Chemical Properties

IACS-010759 is available as a crystalline hydrochloride salt, with the chemical name 5-(5-methyl-1-(3-(4-(methylsulfonyl)piperidin-1-yl)benzyl)-1H-1,2,4-triazol-3-yl)-3-(4-(trifluoromethoxy)phenyl)-1,2,4-oxadiazole hydrochloride salt.

The molecular formula of IACS-010759 hydrochloride salt is  $C_{25}H_{25}F_3N_6O_4S$ .HCl and the molecular weight is 599.024 g/mole (562.564 g/mole as the free base). This compound has not yet been assigned a generic name.

## 3 Study Rationale

#### 3.1 Rationale for IACS-010759 Dose Selection

The starting dose of IACS-010759 has been selected as the human equivalent dose corresponding to no more than 1/10 the no observed adverse effect level (NOAEL) in nonclinical toxicology studies. Additional considerations for dose selection include avoiding Cmax-associated emesis and anticipation of achieving plasma levels associated with preclinical efficacy within a reasonable number of escalation steps. IACS-010759 was well tolerated in 28-day oral toxicology studies in the monkey and rat and the NOAEL in those studies were 1.5 mg/kg/day and 1 mg/kg/day, respectively. Based on these considerations, our projection is that a human starting dose of 0.5 mg will allow a thorough exploration of safety and tolerability in humans while minimizing the exposure of subjects to doses not anticipated to be effective. Using a model based on allometric scaling, a human dose of 0.5 mg, given once daily, would be anticipated to produce a Cmax of ~2.3 ng/mL and to give a projected steady state exposure ratio, animal-tohuman, of approximately 27-fold based on the 1 mg/kg/day dose in the rat and 43-fold based on the 1.5 mg/kg/day dose in the monkey for Cmax and approximately 7-fold based on the rat and 11-fold based on the monkey for AUC. Therefore, the human starting dose of 0.5 mg of IACS-010759, administered orally once daily, would be anticipated to be safe and well tolerated, while allowing attainment early in the dose-escalation studies of doses that may be projected to show benefit in patients.

Limited PK data from subjects in cohorts 1 and 2 showed unexpected levels of accumulation of IACS-010759 throughout the dosing period, consistent with a model in which the clearance of IACS-010759 decreases exponentially with time, leading to an increasingly long terminal  $T_{1/2}$  and accumulation upon multiple dosing. A mathematical model and simulation has been developed based on data from the subjects treated with IACS-010759 to date that predicts the observed human PK. Based on this model, a modified dosing regimen is being implemented for the dose escalation phase with cohorts 3-6 and for the dose expansion phase with cohort 7, consisting of an induction phase in which IACS-010759 is administered daily for up to 7 days, followed by a maintenance phase in which a lower dose is administered weekly to maintain steady state plasma levels (or as otherwise specified by the SMC based on safety, PK and PD data observed).

Page 17 of 59

### 3.2 Rationale for Study Design

Current treatment options for relapsed or refractory AML reflect an unmet medical need and additional options for treatment are needed.

Preclinical data reviewed above strongly suggest a robust antitumor activity with IACS-010759 in AML. The current study focuses on evaluating the maximum tolerated dose (MTD), recommended phase 2 dose (RP2D) and safety profile of IACS-010759 and preliminary clinical efficacy in subjects with confirmed relapsed or refractory AML and no available treatment options with known benefit.

The results from this study will form the basis for decisions for future studies.

## 4 Experimental Plan

## 4.1 Study Design

#### 4.1.1 Study Phase

Phase 1 study with a dose-escalation phase followed by an expansion phase.

#### 4.1.2 Enrollment/Randomization

This open label study will employ a sequential-cohort, non-randomized, single site enrollment. The study will be under ongoing review by a Safety Monitoring Committee (see section 4.1.14).

In the dose-escalation phase, all subjects in a cohort will be monitored for DLT for the first cycle before proceeding with subsequent cohorts. To assess toxicities that may occur beyond cycle 1, cohorts of up to 6 subjects will be assessed following completion of 4 cycles of study drug. If two or more subjects in the cohort did not receive at least 80% of the planned dose due to adverse events, dose escalation will be paused and an evaluation will be performed.

#### 4.1.3 Subject Population

For complete subject eligibility please see section 5.

Dose-escalation phase: Subjects with confirmed relapsed or refractory AML and no available treatment options with known benefit.

Expansion phase: Subjects with relapsed or refractory AML who have failed therapy with up to one prior salvage regimen and no available treatment options with known benefit.

Exception: stem cell transplant [SCT] or stem cell therapy for subjects who previously underwent SCT/stem cell therapy, and are currently in remission will not be considered a salvage regimen.

Relapsed or refractory status is defined by the failure of at least one prior cycle of chemotherapy (including but not limited to cytotoxic chemotherapy, hypomethylator therapy, immune-based therapy, stem cell transplant or stem cell therapy, FLT3-inhibitor therapy, investigational therapy, and others). Patients in first relapse and less than 12 months from diagnosis [short first remission] or in second or later relapse are eligible.

Page 18 of 59

#### 4.1.4 Number of Sites and Subjects

2 to up to 48 subjects will be enrolled at one site.

#### 4.1.5 Sample Size Considerations

The dose-escalation phase of the study will enroll 3-6 subjects in each cohort, based on a 3+3 dose-escalation design to assess the MTD level. A maximum of 36 subjects will enroll in the dose-escalation phase.

A maximum of 18 subjects will enroll in the expansion phase (12 additional subjects and the 6 subjects from the dose-escalation phase at the cohort of the highest dose level shown to be well tolerated or the RP2D). The expansion phase sample size of 18 subjects is not based on a formal sample size calculation. Rather, 18 subjects are deemed to be sufficient for the assessment of safety and tolerability as the primary objective and the exploration of clinical anti-tumor activity and other secondary and exploratory endpoints.

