At the discretion of the sponsor, dose-escalation may be stopped before an MTD is reached. In this case, the RP2D may be chosen based on an assessment of the safety, PK, PD, biomarker, and response data evaluable up to that time. An MTD does not have to be reached to expand a dose cohort if the available data demonstrate that a lower dose level may provide antitumor activity while minimizing potential risk. Upon completion of the dose-escalation, the cohort with either the highest dose level shown to be well tolerated or the RP2D will be expanded to a total of 6 subjects (if not already expanded to 6 subjects due to either observation of a DLT or to further explore safety, PK and PD activity of IACS-010759 at that dose level).

Late onset DLTs that could not be taken into consideration prior to scheduled dose escalations will be ad-hoc evaluated on a case-by-case basis, and may lead to enrollment of additional subjects in specific cohorts or to revision of the previously determined MTD.

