#### 4.1.8 Expansion Phase

Subjects in the expansion phase will be treated at the RP2D level determined in the dose-escalation phase.

The primary objective of the expansion phase is to determine safety of IACS-010759.

Additionally, as part of the expansion phase, the effect of a high fat meal on the PK of IACS-010759 (Food Effect) will be evaluated in a total of 6 subjects (Food Effect cohort), as described in Section 7.1. After the first 6 subjects have been enrolled in the expansion cohort, the next 6 subjects will be enrolled in the Food Effect cohort.

To evaluate safety, the method of Thall, Simon and Estey [20] will be used for monitoring DLTs occurring in the first cycle. The probability of DLT is denoted by  $P_T$ . We assume  $P_T \sim$  beta (0.4, 1.6). Our stopping rule is given by the following probability statement:  $Pr(P_T > 0.20 \mid data) > 0.80$ .

That is, if at any time during the study we determine that there is more than 80% chance that the unacceptable toxicity rate is more than 20% during the expansion phase, then the enrollment will be stopped. Subjects will be monitored by a cohort size of 6 during the expansion phase according to the following stopping boundaries for DLTs, starting from the 12th

subject. The monitoring rule for DLTs, based on these assumptions and monitoring conditions is found in Table 3. For example, accrual in the expansion phase will cease if 4 or more subjects experience DLTs among the first 12 subjects. The operating characteristics are summarized in Table 4. The design software Multc Lean Desktop (version 2.1) developed by the Department of Biostatistics at M. D. Anderson Cancer Center was used to generate the toxicity stopping boundaries and the operating characteristics tables.

Table 3 Stopping boundaries for DLT monitoring

# Subjects evaluated	12	18
# Subjects with DLTs	4-12	6-18

Table 4 Operating characteristics of toxicity monitoring

True DLT Rate	Early Stopping Probability	Average Sample Size
0.10	0.0256	17.8
0.15	0.0922	17.4
0.20	0.2054	16.8
0.25	0.3512	15.9
0.30	0.5075	15.0

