In the expansion phase, after the first 6 subjects have been enrolled in the expansion cohort, the next 6 subjects will be enrolled in the Food Effect group where the effect of a high fat meal on the PK of IACS-010759 will be evaluated on day 1 of cycle 1 for the cohort (Food Effect group). The dose level to be administered will be the single agent RP2D induction dose as determined in the escalation phase or may be lower than the RP2D if clinical safety concerns prevent the use of RP2D for the food effect evaluation. Subjects in the Food Effect group will consume the high-fat meal within 30 minutes *prior to* IACS-010759 administration and blood samples collected at

the timepoints listed in the Study Flowchart for PK analysis. After this day 1 dose, subsequent doses of IACS-010759 will be administered without food as described above for the remainder of the cycle. The plasma levels in these subjects will be compared to those of the other subjects in the expansion cohort to determine whether consumption of a meal affects the plasma levels of IACS-010759.

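### The six escalation subjects counted in the 18-subject expansion set need not have received the RP2D, which conflicts with 4.1.8 and carries into the DLT monitoring

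*Combined protocol and SAP*

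**What the plan says.** Section 4.1.5 sets the size: "A maximum of 18 subjects will enroll in the expansion phase". It composes that number from "12 additional subjects and the 6 subjects from the dose-escalation phase at the cohort of the highest dose level shown to be well tolerated", and then names the RP2D cohort as the other possible source of the six. The Synopsis does the same. Section 4.1.5 adds that "The expansion phase sample size of 18 subjects is not based on a formal sample size calculation", and judges 18 enough for safety, tolerability and exploration of activity.

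Section 4.1.7 repeats the either/or for the cohort that is filled up when escalation ends: "the cohort with either the highest dose level shown to be well tolerated or the RP2D will be expanded to a total of 6". It also foresees that the regimen taken forward may sit below the highest tolerated one, where the data show that "a lower dose level may provide antitumor activity while minimizing potential risk".

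Section 4.1.8 leaves no such choice: "Subjects in the expansion phase will be treated at the RP2D level determined in the dose-escalation phase". The Synopsis has a sentence to the same effect, and Table 2 (4.1.6) lists Cohort 7 as 12 subjects at the RP2D. Section 4.1.8 then monitors first-cycle DLTs in steps of six starting from the 12th subject, with boundaries at 12 and 18 subjects (Table 3) and operating characteristics in Table 4.

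**The concern.** When the highest tolerated cohort is the RP2D, the either/or is harmless. When the RP2D is lower, or is simply a different regimen, the text permits six subjects on another regimen to be counted in a set that 4.1.8 describes as treated at the RP2D. No section says which cohort then supplies the six.

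This reaches the stopping rule. Only 12 expansion subjects are new, so a look at 18 has to include the six carried over. The posterior rule and Table 4 use one DLT probability for everyone counted. With six subjects from elsewhere, the rule no longer answers whether the RP2D has an acceptable DLT rate. The choice would also be open after the cohorts' DLT results are known. Safety, DLTs and the RP2D are primary objectives, so the monitored set should be fixed in advance.

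**Working it through.** **Inputs.** 12 new and 6 carried-over subjects (4.1.5; Table 2); 3 to 6 subjects per escalation cohort (4.1.5); prior beta(0.4, 1.6), stop if Pr(DLT rate > 0.20 | data) > 0.80, looks at 12 and 18 (4.1.8); a tolerated six-subject cohort has at most 1 DLT (4.1.7).

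**1. The plan's own figures.**
- Count: 12 + 6 = 18, and 36 + 12 = 48, as stated.
- Table 3: with r DLTs in n subjects the posterior is beta(0.4 + r, 1.6 + n − r). At n = 12, r = 3 gives 0.608 and r = 4 gives 0.821, so the boundary is 4. At n = 18, r = 5 gives 0.747 and r = 6 gives 0.883, so it is 6. Both agree.
- Table 4: P(X ≥ 4), with X binomial(12, p), gives 0.0256, 0.0922, 0.2054, 0.3512 and 0.5075 for p = 0.10 to 0.30, as tabled. Average size 12q + 18(1 − q), where q is that probability, agrees to within 0.05. Each row uses a single p for all subjects.

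**2. How many subjects are at the RP2D if the six come from another cohort.**
- Within the designated set: 18 − 6 = 12.
- Across the study: the RP2D's own escalation cohort also received that regimen, so 12 + 3 = 15 to 12 + 6 = 18.
- It is 12 study-wide only if the RP2D is a regimen never run as an escalation cohort.

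**3. What those counts mean.** The chance of at least one case of a toxicity with a true rate of 10% is 1 − 0.9^n. The two-sided exact 95% upper limit with no events is 1 − 0.025^(1/n).

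| n | Chance of at least one case | Upper limit, no events |
|---|---|---|
| 18 | 85% | 18.5% |
| 15 | 79% | 21.8% |
| 12 | 72% | 26.5% |

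**4. Share of the monitoring.** At the look at 18, six of 18 (one third) would be on another regimen. If the six are counted first, they are six of 12 (half) at the first look. Section 4.1.8 does not spell out that order; it is the reading suggested by looks at 12 and 18 in a set of 6 + 12.

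**5. Whether the regimens are ordered.** Planned Cycle 1 totals from Table 2, taking six maintenance doses over Days 8 to 21:
- Cohort 4: 7 × 2.5 + 6 × 1.0 = 23.5 mg
- Cohort 5: 5 × 2.5 + 6 × 1.5 = 21.5 mg
- Cohort 6: 5 × 3 + 6 × 2 = 27 mg

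Cohort 4 has the largest induction total (17.5 mg, against 12.5 and 15) and Cohort 6 the largest maintenance total (12 mg, against 6 and 9). Combining cohorts can therefore mix schedules as well as dose levels.

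**The case against.** **The either/or may only name whichever cohort is taken forward.** Read with 4.1.8 and Table 2, it could mean the highest tolerated dose when that is the RP2D, and a lower RP2D otherwise. That may well be the intent. The wording still offers two sources in three places without tying the choice to the RP2D.

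**The plan never promises 18 subjects at the RP2D.** This stands. Section 4.1.5 gives 18 as the expansion size, without a formal calculation. A reader might infer a stated RP2D safety base of 18 from 4.1.8, but no section says it.

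**RP2D data do not normally fall to 12.** This stands too, because the RP2D's own cohort adds 3 to 6. A reader might go below 12 through the Food Effect group, whose dose "may be lower than the RP2D if clinical safety concerns prevent the use of RP2D". That clause is conditional, 6.1 places the evaluation on Day 1 of Cycle 1, and it does not say that later doses are lowered. The documents do not support treating those six as never at the RP2D.

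**The stopping probabilities fall whichever tolerated cohort is carried over.** Correct. If the six bring 0 or 1 DLT and are counted first, four or three more are needed among six new subjects. At a true rate of 0.30 among those six, the chance is 0.07 or 0.26, against 0.5075 in Table 4. An RP2D cohort that passed 3+3 gives the same figures, so this drop cannot be blamed on mixing. The difference is that RP2D subjects would at least inform the rate being judged.

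**Six subjects from a higher dose would make the rule more cautious.** This holds only if DLT risk rises across the regimens. They are not fully ordered, and the answer would still concern a mixture.

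**No pooled RP2D summary is specified.** True: 4.3.2 gives laboratory and vital-sign summaries by cohort, and analysis detail is left to the SAP. The effect on reporting is a risk to close off, not a planned error.

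**Conclusion.** The conflict is in the current text. The Synopsis, 4.1.5 and 4.1.7 allow the six carried-over subjects to come from a regimen other than the RP2D, while 4.1.8 and Table 2 put expansion at the RP2D. It matters only if the RP2D is not the highest tolerated regimen, which 4.1.7 permits but does not predict. In that case 12 of the designated 18 are at the RP2D and the DLT looks judge a mixture. The loss of information about the RP2D is moderate: between none and a fall from 85% to 79% in the chance of seeing a 10% toxicity when the RP2D was run as a cohort, and a fall to 72% only when it was not. These figures assume that all 12 new subjects are enrolled and treated at the RP2D.

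**What to change.** Reconcile the Synopsis, 4.1.5, 4.1.7 and 4.1.8 on three points:

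- The carried-over subjects are those treated at the RP2D regimen. Only they and the new RP2D subjects count in the 18, in the DLT looks at 12 and 18, and in any RP2D summary.
- The fill-up of the highest tolerated cohort in 4.1.7 stays available, but those subjects are not counted in the expansion set when that regimen is not the RP2D.
- If fewer than six escalation subjects received the RP2D, the expansion n and the monitoring boundaries are restated. For example, with three carried over and looks after each six new subjects, the same prior and threshold give stopping at 4 or more of 9 (posterior 0.925; 0.774 at 3) and 5 or more of 15 (0.856; 0.687 at 4).

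State also whether the six are counted before the new subjects. The cost is wording and possibly a smaller stated n. Section 4.1.7 already gives routes to six subjects in a cohort, and the cap of 36 equals six cohorts of six. The change makes the monitored set coherent; it does not restore the Table 4 stopping probabilities, for the reason given above.
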